- 13. Patients who had a liver biopsy performed <= 2 years before enrollment, unless they are willing to undergo all of the trial biopsies, knowing that these biopsies are purely for research and are not clinically indicated. This will be clearly documented in the patients' charts prior to enrollment.
- 14. Patients with coagulopathy (PT/PTT values that are prolonged >= 3 seconds from the upper limit of the normal, including treatment with oral and parenteral anticoagulants), thrombocytopenia (<70,000), abnormal bleeding time or platelet dysfunction will not be enrolled because of potential increase in risk of bleeding with vitamin E treatment. Antiplatelet agents taken for cardiovascular prevention will not exclude patients, unless they cannot be stopped safely for the performance of a liver biopsy.
- 15. Maldigestion or malabsorption that can interfere with absorption of vitamin E including: steatorrhea of all causes, chronic pancreatitis, cystic fibrosis, short bowel syndrome, severe cholestasis, orlistat treatment and similar conditions
- 16. Inability to swallow vitamin E capsules
- 17. Allergy to vitamin E
- 18. Alcohol or substance abuse within the past 12 months. Patients will be required to have an AUDIT score of 7 or less¹⁸, and drink no more than 14 drinks/week (for men) or 7 drinks/week (for women).
- 19. For women of childbearing age, pregnancy or inability (or unwillingness) to practice contraception for the duration of the study or breast feeding.
- 20. Hemoglobin level < 11 g/dL
- 21. History of past or present significant gastrointestinal bleeding, unless treated definitively (i.e. resection, eradication of H. pylori with documentation of ulcer healing, etc).
- 22. Known history of past or present condition that according poses a significant risk for significant gastrointestinal bleeding (i.e. peptic ulcer) unless definitively treated.
- 23. Inability to understand and give informed consent for participation

Monitoring subjects and criteria for withdrawal of subject from the study

Patients will be monitored every 2 weeks during the run-in phase. At this stage, the only intervention is lifestyle modification and no related serious adverse events are anticipated. At this stage, visits that are within 1 week before or after the planned visit date will not be considered a protocol violation.

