After the run-in phase, patients will be admitted for up to 5 days, for the initial biopsies and extended tests as detailed above. At the LDB, it is our standard practice to keep all patients for observation overnight after a biopsy, and to perform a routine complete blood count 6 hours after the procedure. Following discharge, patients will be seen in the

outpatient clinic for the first 3 weeks of treatment, and will be subsequently admitted during the 4th week of treatment, for the second biopsy. At this stage, visits that are within 2 days before or after the scheduled visit date will not be considered a protocol violation. Following the second admission, the patients will be followed in clinic every 4 weeks. From this time point onwards, visits that are within 1 week before or after the planned visit date will not be considered a protocol violation. Patients will be admitted again at the end of the 24 week period for another extensive evaluation. During the extended treatment phase, patients will be seen every 12 weeks.

Patients will also be monitored as appropriate for patients with liver disease. Specifically, patients with liver cirrhosis or high-risk for hepatocellular carcinoma (HCC) will undergo surveillance for HCC by ultrasound or cross sectional imaging every 6-12 months, or according to most current guidelines. Patients with cirrhosis will be monitored by endoscopy as appropriate for the development of esophageal varices.

Patients who become pregnant during the study will be withdrawn, as pregnancy and associated hormonal and metabolic changes may affect hepatic fat metabolism and will confound the analysis. Patients who do not respond to treatment by week 48 will be withdrawn for futility. There are no other pre-specified criteria for withdrawal of patients from the study. Patients will be withdrawn if, according to the best judgment of the treating physician or the principal investigator, continuing treatment poses an unacceptable risk to the patient.

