Patients with hemoglobin < 10 g/dL will not undergo the FSIVGTT test and/or collection of blood for NK/NKT cells. Patients with hemoglobin < 10 g/dL will not undergo the first (baseline) liver biopsy. That biopsy may be deferred for up to 4 weeks if the anemia can be treated sufficiently by that time. Patients who cannot undergo the baseline liver biopsy will be withdrawn from the study. Patients with hemoglobin < 10 g/dL will not undergo the second or third liver biopsy; these biopsies will not be deferred but the patients may continue on the study.

Vitamin E for Non-Alcoholic Fatty Liver

Table 1 – Monitoring and investigation schedule

Phase	Visit week	Vit E dose	Nurse ¹	MD	Nutritionist ²	Routine labs ³	Extended labs ⁴	NK/NKT cell studies ⁵	Liver & Adipose Tissue Biopsy	FSIVGTT ⁶	Imaging	Breath Test	Questionaires
Enrollment	(-4) – (-1)		+	+		+							DHQ II, IPAQ, 3-day food
Run-in	0		+		++	+	+	+			MRS, MRI		Symptom, quality of life
	2				++, +								
	4		+		+	+							
	6				+								
	8		+		+	+							
	10				+								
Admission	12		+	+	++	+	+	+	+	+	MRS, MRI, DEXA	+	3-day food, IPAQ, symptom, quality of life
Randomized Rx	0 (1-2 wk later)	200/400/800	+	+		+							
	1	200/400/800	+			+							
	2	200/400/800	+			+							
	3	200/400/800	+			+							
2 nd Admission	4	200/400/800	+			+	+	+	+	+	MRS		
	8	200/400/800	+	+	++	+							
	12	200/400/800	+			+	+						symptom
	16	200/400/800	+	+	++	+							
	20	200/400/800	+			+							
3rd Admission	24	800	+	+	++	+	+	+		+	MRS, MRI, DEXA	+	3-day food, IPAQ, symptom, quality of life
Extended Rx	36	800	+	+	++	+							
	48	800 (or lower ⁷)	+	+	++	+	+				MRS		3-day food, IPAQ, symptom, quality of life
	60-132 (q12 wks)	800 (or lower ⁷)	+	+	++	+	+ (q24 wks)						3-day food, IPAQ, symptom, quality of life (q 24 wks)

Vitamin E for Non-Alcoholic Fatty Liver

Exit Admission	144	Stop	+	+	++	+	+	+5	+	+	MRS, MRI, DEXA,	+	3-day food, IPAQ, symptom, quality of life

¹ Nursing visit – includes vital signs, weight, list of current study and non-study medications and nursing assessment

² Nutrition visit - + marks group session, ++ marks individual session

³ Routine labs – complete blood count, Chem-20, serum insulin, c-peptide, free fatty acids, lipid panel, vitamin E level, research blood (total volume 31.5 ml)

⁴ Extended labs – GGT, PT, PTT, HbA1c, CRP, Thyroid panel, apolipoproteins, ferritin, iron, transferrin saturation, immunoglobulins, PSA, research plasma (total volume 52.5 ml with Routine labs), urinalysis

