As some studies suggest an effect of vitamin E on platelet aggregation⁴², and given the possible association with hemorrhagic stroke, we exclude patients with high bleeding risk, such as those with coagulopathies, use of anticoagulants, thrombocytopenia or known platelet dysfunction. Furthermore, due to the possibility of increased risk of gastrointestinal bleeding, patients with a pre-existing history of iron deficiency anemia secondary to gastrointestinal sources are excluded. On the other hand, vitamin E supplementation is not associated with changes in standard parameters of bleeding tendency, including PT, PTT,

platelet count and bleeding time^{43, 44}, rendering these useless as a tool for safety monitoring during vitamin E treatment. However, if during the study the platelet count or PT/PTT cross the thresholds for study inclusion (i.e. platelets <70,000, PT/PTT prolonged by >=3 seconds), treatment will be stopped and patients withdrawn from the study.

Recently, data from extended follow-up of the SELECT trial⁴⁵ suggested increased risk for the diagnosis of prostate cancer in patients treated with vitamin E. This is in contrast to the findings of two other similar studies^{46, 47} which did not show such an effect. Our patients are anticipated to be significantly younger than the study population in SELECT (median age 62); furthermore, risk for prostate cancer appeared to increase numerically only after more than 3 years of treatment. We will monitor PSA levels every 12 months on male patients in our study. Screening for prostate cancer may lead to further evaluation of abnormal results, including referrals, blood tests and possible invasive procedures. There is also a risk of detecting prostate cancers that are not destined to become clinically significant. The risks and benefits of screening with annual PSA testing will be discussed with all male participants prior to enrollment and patients will have the option to elect not to be screened.

Adverse event reporting and data monitoring

Reportable events will be tracked and submitted to the IRB as outlined in Policy 801.

The PI will immediately report SAEs to the Sponsor according to the requirements of 21 CFR 312.64(b) and as agreed upon with the sponsor. The PI will record nonserious AEs and report them to the Sponsor according to the timetable for reporting specified in the protocol (21 CFR 312.64(b).

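### The risk section orders withdrawal at set platelet and PT/PTT limits and names an anemia exclusion; the withdrawal section and the numbered exclusions contain neither

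*Combined protocol and SAP*

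**What the plan says.** **Withdrawal.** The section on monitoring subjects and criteria for withdrawal gives two criteria: "Patients who become pregnant during the study will be withdrawn" and "Patients who do not respond to treatment by week 48 will be withdrawn for futility". The next sentence reads "There are no other pre-specified criteria for withdrawal of patients from the study". A discretionary clause follows: "Patients will be withdrawn if, according to the best judgment of the treating physician or the principal investigator, continuing treatment poses an unacceptable risk". Later in the same section, in the text on low hemoglobin, comes "Patients who cannot undergo the baseline liver biopsy will be withdrawn from the study".

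Under Risks and Discomforts, the vitamin E treatment paragraphs say that if the platelet count or PT/PTT crosses the entry thresholds during the study (platelets below 70,000; PT/PTT prolonged by 3 seconds or more), "treatment will be stopped and patients withdrawn from the study". The figures match numbered exclusion 14.

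**Eligibility.** The same risk text says that, because of possible gastrointestinal bleeding, "patients with a pre-existing history of iron deficiency anemia secondary to gastrointestinal sources are excluded". In the numbered list, item 20 excludes hemoglobin below 11 g/dL. Item 21 excludes "History of past or present significant gastrointestinal bleeding, unless treated definitively". Item 22 excludes conditions carrying a significant risk of such bleeding, again with an exception for definitive treatment.

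**The concern.** A withdrawal section that declares its list complete will be read as complete. If another section holds a further mandatory safety rule, two physicians working correctly from different pages can treat the same laboratory result differently. The eligibility text has the same weakness: the risk section presents the anemia exclusion as one of the measures that limit bleeding risk, but the list used to judge eligibility does not contain it.

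Both points concern bleeding in a trial with percutaneous liver biopsy on treatment, at week 4 for all patients and at week 144 for those who take the optional extension. There is a smaller statistical interest as well. Mandatory withdrawal produces missing end-of-treatment values, and a reader of the withdrawal section would not know that this source exists.

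**Working it through.** No arithmetic applies. The check sets the passages side by side.

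**1. Withdrawal rules, by place and timing**

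| Rule | Where stated | Acts when | Nature |
|---|---|---|---|
| Pregnancy | Withdrawal section, before the closing sentence | Any time | Mandatory |
| Non-response at week 48 | Withdrawal section, before the closing sentence | On treatment | Mandatory |
| Unacceptable risk | Withdrawal section, after the closing sentence | On treatment | Judgment, no laboratory limit |
| Baseline biopsy not possible | Withdrawal section, later paragraph | Before vitamin E | Mandatory |
| Entry biopsy without NAFLD | Vitamin E Treatment; Liver biopsies (design justification) | Before vitamin E | Mandatory |
| Platelets or PT/PTT past the entry limits | Risks and Discomforts | On treatment | Mandatory |

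Three pre-specified rules contradict the closing sentence as written. Two of them act before any vitamin E is given, and one of those two already stands in the withdrawal section. That leaves one mandatory on-treatment safety rule missing from the section. Platelets and PT/PTT count as one rule because they share one sentence and one consequence.

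**2. The same result under each text.** Take a patient on vitamin E whose platelet count falls below 70,000. Under Risks and Discomforts, treatment stops and the patient leaves the study. Under the withdrawal section, no pre-specified criterion is met, and the patient leaves only if a physician or the investigator judges the risk of continuing unacceptable. The first text is automatic and the second is discretionary.

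**3. Can it arise?** Table 1 includes a complete blood count in the routine labs and PT/PTT in the extended labs, which on treatment fall at weeks 4, 12, 24 and 48, then every 24 weeks, and at week 144. Numbered exclusion 6 bars only decompensated advanced liver disease, and the withdrawal section plans surveillance for patients with cirrhosis. Results past the limits are therefore possible and would be seen.

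**4. A source of ambiguity.** Immediately before setting the rule, the risk text dismisses PT, PTT, platelet count and bleeding time as of no use for monitoring safety on vitamin E. It does not say why two of these measures then govern withdrawal.

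**5. Eligibility test case.** Take a patient with past iron deficiency anemia from a gastrointestinal source that was definitively treated, and hemoglobin of 11 g/dL or more.

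- Item 20: not met, because hemoglobin is not below 11 g/dL.
- Items 21 and 22: not met, because each exempts definitive treatment.
- Risk text: met, because it rests on history and carries no exception.

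The list admits this patient and the risk text excludes the same patient. The result is the same if the blood loss was never significant and no item 22 condition exists.

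**The case against.** The strongest reply is that the withdrawal section does provide for safety. Its discretionary clause lets a physician withdraw a patient whose platelets or PT/PTT cross the limits, and the Monitoring section adds weekly investigator meetings and routine review of laboratory results. A reader might infer that staff following the withdrawal section are told to keep such a patient. The documents do not support that, because the section permits withdrawal and only fails to require it.

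A reader might also infer that the two texts cannot both be followed. That goes too far. The closing sentence describes the list and forbids nothing, so withdrawing a patient under the risk text breaches no instruction. Likewise, applying the anemia exclusion enrols nobody whom the numbered list bars.

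The biopsy rules should not be used to inflate the count, since they are not on-treatment safety triggers. Biopsy also has its own protections in exclusion 12 and the hemoglobin limit of 10 g/dL, and PT/PTT is scheduled at weeks 4 and 144. Finally, the anemia phrase may be a loose paraphrase of items 20 to 22, which cover most of the same patients.

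These replies narrow the point without removing it. Discretion is not the same as a mandatory threshold, and a history without exception is not the same as a history with one.

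**Conclusion.** The point holds as two separate inconsistencies of wording, linked only by the bleeding-risk text.

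First, one mandatory on-treatment rule, on platelets and PT/PTT, is absent from a section that says its criteria are complete. Physicians working from that section could properly retain a patient whom the risk text requires to be withdrawn. The closing sentence is also literally wrong for the two pre-treatment biopsy rules, which matters less.

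Second, one stated exclusion is missing from the 23 numbered items. The gap is confined to patients with hemoglobin of at least 11 g/dL whose source was definitively treated or not significant.

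The documents give no count of patients affected. That it is probably small is a judgment, resting on the overlap of items 14 and 20 to 22 with the risk text. The sample size calculation uses assumed response rates with an allowance for drop-out, so neither point changes it. The conclusion assumes that both sections are current and that neither overrides the other; the documents state no order of precedence.

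**What to change.** 1. Reconcile the withdrawal section with the vitamin E text under Risks and Discomforts, so that a platelet or PT/PTT result past the limits has one stated consequence. The withdrawal section should state every pre-specified trigger that applies.
2. Correct the closing sentence to allow for the two pre-treatment rules: baseline biopsy not possible (already in that section), and entry biopsy without NAFLD (in Vitamin E Treatment and in the design justification for liver biopsies).
3. Reconcile the anemia statement in the risk text with exclusions 20 to 22, so that both define the same eligible patients, including those with a treated or minor source.
4. If the laboratory rule is kept, explain it alongside the statement that these measures are of no use for monitoring.

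Which rule and which limits apply is for the sponsor to decide. The cost is a wording amendment, with no effect on the visit schedule, sample size or analysis.

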We propose a phase IIa study to determine the optimal dose of vitamin E and its mechanism and site of action. In this study we aim to enroll up to 90 patients with NAFLD. Initially, all patients will undergo 12 weeks of intensive lifestyle modification. Following that, all patients will be randomized to treatment with 3 different doses of natural vitamin E (rrr- α -tocopherol at 200, 400 or 800 IU/d) for 24 weeks. The primary end points for efficacy are normalization of liver enzymes and reduction in liver fat contents by magnetic resonance spectroscopy. Patients will undergo liver and adipose tissue biopsies before vitamin E treatment and after 4 weeks of therapy, and the biopsy samples will be used to measure changes in gene expression and markers of oxidative stress. This will be coupled with extensive phenotyping before and after treatment using serological, radiological and dynamic endocrine testing and is aimed at finding the dose-response characteristics of vitamin E in NAFLD, and allowing us to understand the mechanism of its action.

After 24 weeks of randomized treatment, all patients will be switched to a dose of 800 IU/ml and will continue treatment for up to 30 months, at the end of which another liver biopsy will be performed. From this phase we will assess the effects of dose increase of vitamin E on liver enzymes and fat content, and will determine the effect of long-term treatment on histological outcome.

Table of Contents

Précis	3
Table of Contents	4
Introduction	6
Non-alcoholic fatty liver disease	6
Vitamin E	7
Vitamin E for NAFLD	8
Aims	10
Primary Aims:	10
Secondary aims:	10
Study design and methods	11
Overall design (Figure 3)	11
Initial screening and enrollment	12
Run-in phase and lifestyle intervention	12
Detailed in-patient assessment	14
Vitamin E Treatment	15
Extended Treatment Phase	16
Details of procedures	18
Adipose Tissue Biopsy	18
Liver Biopsy	18
Magnetic Resonance Spectroscopy	19
Justification for study design	19
Run-in phase	19
Liver biopsies	20
Absence of a control arm	21
Duration of treatment	21
Inclusion and exclusion criteria	21
Inclusion	21
Exclusion criteria	
Monitoring subjects and criteria for withdrawal of subject from the study	
Analysis of the study	
End points	27

Vitamin E for Non-Alcoholic Fatty Liver

Primary end points	27
Secondary end points	27
Basic scientific end points	27
Statistical analyses	28
Sample size calculation	28
Human subject protections	28
Rationale for subject selection	28

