⁵ NK/NKT cell analyses – On Run-in phase, first admission and week 144 will be drawn for all patients. On weeks 4 and 24 these will be performed only on the 200 IU/d and 800 IU/d arms (total volume 48 ml). On week 144 only 30 ml will be obtained. Will not be performed if Hb < 10 g/dL.

⁶ FSIVGTT – total blood volume drawn 120-150 ml. Will not be performed if Hb < 10 g/dL.

⁷ Possible lowering of vitamin E dose based on week 48 results (see Figure 4).

Analysis of the study

End points

Primary end points

There are two primary clinical end points in the study. The primary biochemical response is defined in a binary manner as an end-of-treatment AST <=32 or ALT <=35 U/L. The selection of these cut-off values is based on a pilot analysis by us that examined in an unbiased manner several rules for biochemical response and found this to be the one most strongly associated with histological response to treatment, irrespective of treatment modality³¹. We will also analyze the absolute change in ALT and AST from pre-treatment to end-of treatment as continuous parameters of the effect of treatment on liver enzymes. Patients who at the time of starting vitamin E treatment have normal liver enzymes will be excluded from this analysis. The primary physiological response is the absolute change in liver fat content as determined by comparing the ¹H-MRS results from pre-treatment to end of treatment.

Secondary end points

Secondary end points include: absolute and percent decrease in liver enzymes, decrease in GGT levels, percent reduction in liver fat.

A secondary analysis will analyze the effect of the lifestyle modification by comparing the end points between enrollment and the end of the lifestyle modification phase. Another analysis will determine the effect of increasing the dose of vitamin E by comparing the end points between the end of the randomized phase (week 24) to weeks 24 and 144 of the extended phase.

The kinetics of response will be determined by analyzing sequential ALT and AST measurements. Current data suggest biphasic response pattern to vitamin E and mathematical modeling will be applied to the results and will be compared between doses. Similar modeling will be applied to changes in liver fat content by ¹H-MRS.

Basic scientific end points

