Gene expression in liver and adipose tissue will be analyzed using microarray and quantitative PCR (qPCR) of tissue samples. Treatment-induced changes or comparisons between groups of patient (i.e. comparison of baseline expression between responders and non-responders) will be expressed as fold-induction.

NK and NKT cell changes in the serum and liver tissue will be analyzed using phenotyping and functional assays.

Oxidative stress will be measured in the serum, urine, liver and adipose tissue using TBARS assay, F₂-isoprostanes, 9-HODE, 13-HODE, SOD activity or similar measures. In women of child-bearing age, the phase of the menstrual cycle will be recorded on extended visits, as F₂-isoprostane levels can be affected by it.

Statistical analyses

Parameters of response to treatment will be analyzed by matched-pair comparison between pre-treatment and end of treatment values. Student's t-test will be used for values that are distributed normally while Wilcoxon's sign-ranked test will be used for non-parametric values. Categorical comparisons will be performed using X^2 or Fisher's exact test, as appropriate. The Cochran-Armitage test for trend will be used to test for a dose effect on the primary clinical end points.

To determine the effect of genetic variants, genotype-based analyses will be preferred to allelic analyses, with an additive model used primarily, unless other (dominant or recessive) models seem more appropriate. Linear or ordinal logistic regression will be used.

All analyses will be done with and without stratification for the presence of diabetes mellitus.

An $\alpha \le 0.05$ will be used to determine statistical significance.

Sample size calculation

The main goal of the study is to understand and characterize the mechanism of response to vitamin E. An important goal of the study is to simultaneously collect liver and adipose tissue to determine the site of action of the vitamin E and the relative contribution of each tissue to the disease. For most of the planned end points, including changes in liver fat content by ¹H-MRS and the basic scientific end points, there is not enough pre-existing data to allow for accurate sample size calculation.

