For the comparison of effectiveness between different doses of vitamin E (primary aim 1), the primary biochemical end point will be used. We assume a response rate of 45% with the 800 IU/d dose (similar to that seen at the PIVENS trial), a 10% response rate to the 200 mg/d dose and a 20% response to the 400 mg/d dose. Under these assumptions, a sample size of 25 patients per group will give a power of 80% to detect a linear trend with statistical significance of 5% (Cochran-Armitage test). To account for possible drop-out and loss to follow-up, we are aiming to recruit 30 patients per group or an overall of 90 patients in the study.

As the sample size calculation is limited by the absence of published data, we will re-assess our calculations after 10 patients have been enrolled in each arm, and again after 20 have been enrolled

Human subject protections

Rationale for subject selection

The study is designed to enroll patients with NAFLD that can be potentially benefit from treatment. Currently, there are no reliable non-invasive markers that accurately distinguish NASH from steatosis only, although the latter seems to carry a more favorable prognosis. For patients with steatosis only, it is unclear whether treatment can improve their disease and prevent progression to NASH. In most clinical trials with histological end points, patients with steatosis only were excluded as they cannot show significant histological

improvement. In this study, with a primarily scientific outcome, we are interested in studying the effect of vitamin E on these patients as well and we consider the intervention to be low-risk enough to allow us to recruit all patients with NAFLD.

The exclusion criteria for the study are mainly geared towards limiting enrollment to patients for whom treatment is considered safe and that have no confounders that would limit the analysis of the results. There are no limitations based on race or ethnicity. However, we anticipate that very few patients of African ancestry will be enrolled, because of the scarcity of NAFLD in these patients and their apparent "protection" from liver fat accumulation.

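### Two unranked primary end points share one 5% level with no success rule; if either may carry the dose claim, the false-positive chance can reach 9.75%

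*Combined protocol and SAP*

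**What the plan says.** The précis names two efficacy end points side by side: "The primary end points for efficacy are normalization of liver enzymes and reduction in liver fat contents by magnetic resonance spectroscopy". The Primary end points section does the same: "There are two primary clinical end points in the study". The first is binary: "The primary biochemical response is defined in a binary manner as an end-of-treatment AST <=32 or ALT <=35 U/L". The second is continuous: "The primary physiological response is the absolute change in liver fat content as determined by comparing the" spectroscopy results before and at the end of treatment. Neither is placed ahead of the other.

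Under Statistical analyses, the Cochran-Armitage trend test is assigned to the dose effect on the primary clinical end points, in the plural, and one threshold covers everything: an alpha of 0.05 or less "will be used to determine statistical significance".

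Sample size calculation then takes a narrower line. For comparing doses, which it labels primary aim 1, "the primary biochemical end point will be used".

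The continuous changes in ALT and AST are described within the Primary end points section as a further analysis. They appear again in the next section: "Secondary end points include: absolute and percent decrease in liver enzymes".

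**The concern.** The stated primary clinical aim is to define the optimal dose, and the trial is sized on a formal 5% trend test. A reader of the results needs to know which test decides that aim. Statistical analyses allows a dose effect to be looked for on two end points at 5% each. Sample size calculation implies that only one of them counts. Nothing says whether a positive result on liver fat alone, with a null result on enzymes, would be reported as a primary dose effect. If it would, the 5% attached to the dose conclusion is not the error rate that applies.

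Two smaller gaps make this worse. The Cochran-Armitage test is for a binary outcome, so the dose test for the continuous liver fat change is in effect undefined. The absolute change in ALT and AST also has an unclear status, because it is described under one heading and listed under the other.

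**Working it through.** **1. The plan's own figure.** Inputs from Sample size calculation: response rates of 10%, 20% and 45% for the low, middle and high dose, 25 patients per group, Cochran-Armitage test at 5%, 80% power. The sidedness is not stated; I take two-sided. With scores s, mean score s̄ and mean rate p̄ = 0.25:

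- T = n Σ p(s − s̄)
- V0 = n p̄(1 − p̄) Σ(s − s̄)²
- V1 = n Σ p(1 − p)(s − s̄)²
- power = Φ[(T − 1.96√V0)/√V1]

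Equally spaced scores 0, 1, 2 with n = 25 give T = 25 × 0.35 = 8.75, V0 = 25 × 0.375 = 9.375 and V1 = 25 × 0.3375 = 8.4375. Then (8.75 − 1.96 × 3.062)/2.905 = 0.946, which is 82.8% power. Dose-proportional scores 2, 4, 8 give 83.8%. The conditional exact test gives 79.7% and 81.2%. The plan's 25 per group for 80% is therefore reproduced as a two-sided test of the biochemical end point alone at the full 5%.

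**2. Error rate if either end point counts.** For two independent tests at 5%: 1 − 0.95² = 9.75%. For test statistics with correlation ρ, using a bivariate normal, it is 1 − P(|Z1| < 1.96 and |Z2| < 1.96):

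| ρ (assumed) | chance of at least one false positive |
|---|---|
| 0 | 9.75% |
| 0.3 | 9.5% |
| 0.5 | 9.1% |
| 0.8 | 7.8% |
| 0.9 | 7.0% |

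The documents give no correlation. Both end points come from the same patients, so some positive correlation is plausible, which is why 9.75% is stated as an upper figure.

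**3. Error rate if both must succeed.** A false claim then needs the test of a truly null end point to be significant, which happens at most 5% of the time.

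**4. Error rate if only the biochemical end point decides aim 1.** One test at 5%, so 5%.

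**5. Cost of the two usual remedies.**

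- *Bonferroni, 2.5% each.* Replacing 1.96 by 2.241 in step 1, power at 25 per group falls to 74.2% (equal scores) or 75.9% (dose scores), and 80% power needs 29 or 28 evaluable per group.
- *Fixed sequence, biochemical test first.* The family-wise error is at most 5%, and the biochemical test keeps the power in step 1.

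**6. Sensitivity of the fixed sequence to lost patients.** Patients with normal enzymes when vitamin E starts are excluded from the enzyme analysis. The increase from 25 to 30 per group is explained only by drop-out and loss to follow-up. With 20 evaluable per group (an illustration, not a forecast) and equal scores, (7.00 − 1.96 × 2.739)/2.598 = 0.628, or 73.5% power. Dose scores give 75.0%.

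**The case against.** The strongest reply is that Sample size calculation already answers the question. It ties the dose comparison to the biochemical end point, so the dose conclusion rests on one test at 5%. Liver fat could belong to the second primary aim, the mechanism of fat loss, and whether to adjust across separate aims is a matter of judgement. The trial is also phase IIa, its main goal is described as mechanistic, and the plan never promises a family-wise 5%.

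Much of this stands. It rules out the stronger reading that a reader might infer, namely that the trial's error rate simply is 9–10%. That figure needs success on either end point to count and the correlation to be no more than about 0.5, and the documents state neither. What does not stand is that the matter is settled. The sentence on the biochemical end point is a basis for sizing, not a testing order. The link between liver fat and the mechanistic aim is nowhere stated, and Statistical analyses still directs the dose test at both end points.

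A second tempting reading is that there are four primary tests, counting ALT change and AST change. The documents do not support it: the section says there are two, presents the continuous changes as an additional analysis, and the absolute decrease is listed as secondary. That overlap calls for tidying and should not enter the error calculation.

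**Conclusion.** The point holds as an unresolved ambiguity with a bounded consequence. Two primary end points are unranked, share a blanket 5% level and have no success rule, and two sections point to different bases for the dose conclusion. If either end point may carry the claim, the false-positive chance is between about 7.0% and 9.75% for correlations from 0.9 down to 0. If both must succeed it is at most 5%, and if the biochemical end point alone decides it is 5%. These figures assume one two-sided test per end point. They do not cover the repetition of every analysis with and without stratification for diabetes. The early phase lowers the stakes, but the trial was sized on a formal 5% test for its dose aim, so the plan should say which result decides that aim.

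**What to change.** Amend the précis, Primary end points, Statistical analyses and Sample size calculation so that they agree:

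1. The trend test on biochemical response is the single primary test for aim 1, at 5%. State its sidedness, its dose scores, and whether the version with or without diabetes stratification decides.
2. The dose effect on liver fat change is tested second, at 5%, and only if the first test is significant. Replace Cochran-Armitage here with a trend test for a continuous outcome, for example linear regression of the change on dose, adjusted for baseline liver fat.
3. Continuous ALT and AST change are listed once, as secondary.

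This takes a few sentences. It turns what the sample size section already implies into a rule and leaves the planned 25 evaluable per group unchanged. Liver fat has no power calculation of its own, so no stated power is given up by placing it second. The real cost is that liver fat can be reported only as supportive if the biochemical test fails. That becomes more likely if the normal-enzyme exclusion leaves fewer than 25 evaluable per group: about 74–75% power at an illustrative 20, even if the assumed response rates are true. The sponsor should accept that openly or allow for the exclusion in the recruitment target.
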